### Inclusion criteria:

$\geq 18$  years of age

Taking  $\geq 1$  ocular hypotensive medication with a diagnosis of any kind of glaucoma, suspected glaucoma or ocular hypertension.

Did not opt-out from recruitment letter.

Able to instill eyedrops themselves.

Have a phone- cell or landline.

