**Exploratory Outcome:** Intraocular Pressure (IOP). Change in IOP between the baseline and exit visit will be assessed. We will measure IOP in both arms using the iCare (Tiolat Oy, Helsinki, Finland), a method that does not require corneal anesthesia. The iCare has been shown to correlate well with gold standard IOP measurement by Goldmann applanation tonometry. We will obtain three reliable (assessed by iCare) measures of IOP at each study visit and use the median as the study visit IOP which will be recorded both in the REDCap database and in the electronic health record to communicate with the participants' ophthalmologist. IOP control greatly reduces vision loss from glaucoma and is used as a surrogate marker of glaucoma control in drug and device trials and in clinical practice. However, given the short duration of the SEE Program, we would expect this intervention to cause at most a small reduction in IOP from baseline to six months, even if diurnal measures of IOP or obtaining IOP at a set time were feasible, which is not the case. We are not powered to detect small changes in IOP. Assessing whether there is a trend toward lower IOP in intervention participants will inform future larger scale trials with a measure of IOP control as a primary outcome.

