### **Statistical Analysis Plan**

We will perform intent-to-treat analysis of all randomized participants to evaluate our primary, secondary and exploratory outcomes. We will compare the primary outcome variable, mean adherence, between the two groups using ANOVA, blocking on clinic. We will also analyze the proportion of subjects achieving  $\geq 80\%$  adherence between the treatment group and control group, with the Cochran-Mantel-Haenszel Test for equality of proportions. We will use Student's t-test on post-trial, 12-month medication possession ratios to assess longer-term effects of the SEE Program compared to enhanced standard care.

Additionally, we will use pre-trial medication possession ratios in ANCOVA to investigate whether treatment effectiveness is steady across different levels of pre-trial adherence. We will conduct a sensitivity analysis to test mean adherence between the two groups with ANOVA, blocking on clinic. To investigate trends in adherence over time, we will calculate adherence monthly. Spaghetti plots will visualize trends within the treatment and control groups (linear, step, decaying effect, etc.). Linear regression will test for trends of adherence over time by treatment group.

For the secondary outcome of glaucoma related distress (GRD), we will score the scale according to the measure's documentation at the baseline and exit visits and calculate change. Descriptive statistics and plots will be generated to understand the distribution of scores and change, overall and stratified by treatment group and clinic. The exit GRD score will be regressed on treatment group, adjusted for baseline GRD and clinic.

For the exploratory IOP outcome, exit IOPs will be analyzed using measures from both eyes. The distribution of IOP and IOP change will be assessed with descriptive statistics and plots. The effect of treatment on IOP will be assessed with a linear mixed regression model, adjusting for baseline IOP and clinic, and controlling for the correlation between eyes of a subject with a random subject effect.

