### **Sample Size Aim 1: Compare the efficacy of the SEE Program with enhanced standard care in improving glaucoma medication adherence.**

We conducted brief interviews with 25 glaucoma specialists from throughout the US to gauge expert opinion regarding clinically important effect size. Their average recommendation for difference of group proportions of good adherence was 18.5 percentage points (95% CI 15.6-

21.5). Their average recommendation for difference of group mean adherence was 17.7 percentage points (95% CI 14.6-20.8). Additionally, mean medication adherence increased by 20 percentage points in our SEE Program pilot study from 65.7% ( $\pm 10.3$ ) at baseline to 85.7% ( $\pm 11.8$ ) after the program. With 97 participants in each group, a t-test has 80% power to detect a difference of 8 percentage points in mean adherence between the two groups, if the within group standard deviation (SD) is 20 ( $0.40 \times 20 = 8$ ). In our preliminary data the SD was 18, but we anticipate and plan for a possibly more diverse study group (calculated using R 'pwr' package). Our glaucoma specialists were divided on the importance of clinically important effect size, so we plan to be adequately powered for both continuous and binary adherence measures. Their average recommendation for difference of group proportions of good adherence was 18.5 percentage points (95% CI 15.6-21.5). The proposed sample size (n=97 per group) provides 80% power (at two-sided  $\alpha=0.05$ ) for Pearson's Chi Square Test of Independence to find a difference of 20 percentage points for the proportion of patients attaining good ( $\geq 80\%$ ) adherence between the intervention and control groups.

For our secondary outcome, with this sample size, we can detect a 1.1-point difference in mean change in Glaucoma Related Distress (scale 6-18) between trial arms if the SD is 2.8, as it was in our preliminary data. For this sample size in our exploratory outcome, we can detect a 1.9 mmHg difference in mean change in IOP between trial arms if the SD is 4.6 mmHg, as it was in our preliminary data. Although we will make concerted efforts to maximize retention, we will prepare for up to a 20% loss to follow-up as was experienced in our preliminary study and will enroll 115 participants in each arm for a total of 230 participants.

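### The exploratory IOP model uses both eyes of every participant, so if some participants are prescribed drops in one eye only, the estimated effect shrinks toward zero

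*Combined protocol and SAP*

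**What the plan says.** The Statistical Analysis Plan states that "exit IOPs will be analyzed using measures from both eyes". The model is a linear mixed regression, "adjusting for baseline IOP and clinic" and "controlling for the correlation between eyes of a subject with a random subject effect". The opening sentence of the same section sets the population: "We will perform intent-to-treat analysis of all randomized participants".

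The Inclusion criteria work at the level of the person. They ask for at least one "ocular hypotensive medication with a diagnosis of any kind of glaucoma, suspected glaucoma or ocular hypertension". Neither the inclusion nor the exclusion list says whether one eye or both must be treated.

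Under OUTCOMES, the IOP paragraph takes three readings at each visit and will "use the median as the study visit IOP", without mentioning the eye. It labels IOP exploratory, expects at most a small reduction over six months, and adds: "We are not powered to detect small changes in IOP". Its stated purpose is to look for a trend that would inform larger trials with IOP control as the primary outcome. The Aim 1 sample size section says that "we can detect a 1.9 mmHg difference in mean change in IOP between trial arms if the SD is 4.6 mmHg".

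No section limits the IOP analysis to treated eyes, adds eye-level treatment status to the model, or says that the treated eye is recorded.

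**The concern.** The programme is meant to act on IOP mainly through better use of prescribed drops. An eye with no prescribed drop has no adherence to improve, yet the model gives it the same standing as a treated eye. Adjusting for baseline IOP deals with starting level, and the random subject effect deals with correlation between eyes. Neither removes the averaging of an effect in treated eyes with little or no effect in untreated ones.

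At stake is the trend read-out that this outcome exists to provide. The plan already expects a small effect, and further shrinkage makes it harder to see. It could also mislead the sizing of a later trial that analyses treated eyes, because the required sample size varies with one over the square of the effect.

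**Working it through.** **Inputs from the documents** (Aim 1 sample size section): 97 evaluable participants per arm, SD of IOP change 4.6 mmHg, detectable difference 1.9 mmHg. The 80% power and two-sided 5% level are stated there for adherence and are taken to apply to IOP.

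**Input not in the documents:** u, the share of participants prescribed drops in one eye only. It is assumed at 10%, 20% and 40%. With two eyes each, these correspond to 5%, 10% and 20% of analysed eyes.

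**Step 1. Reproduce the plan's figure.** Standard error of the arm difference = 4.6 × √(2/97) = 0.66 mmHg. Detectable difference = (1.96 + 0.84) × 0.66 = 1.85 mmHg by the normal approximation, or 1.86 by the t-test. Both round to the stated 1.9. Power at exactly 1.9 is about 82%.

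**Step 2. Dilution.** Arm is a between-person factor. With two eyes per person and a random subject effect, the arm coefficient is therefore the difference in person-level averages over both eyes. Let δ be the effect in a treated eye, and take the effect in an untreated eye as zero. A person treating both eyes contributes δ and a person treating one contributes δ/2, so

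expected estimate = (1 - u)δ + u(δ/2) = δ(1 - u/2).

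| u | factor | δ = 1.9 | t-test power at the diluted value | δ = 1.0 |
|---|---|---|---|---|
| 0 | 1.00 | 1.90 | 82% | 1.00 |
| 10% | 0.95 | 1.81 | 78% | 0.95 |
| 20% | 0.90 | 1.71 | 73% | 0.90 |
| 40% | 0.80 | 1.52 | 63% | 0.80 |

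The power column treats 4.6 as the SD of the person-level quantity. The 1.0 mmHg column is only an illustration of a smaller effect.

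**Step 3. Check by simulation.** A mixed model was fitted to 60 simulated trials for each u, with 97 per arm, a true treated-eye effect of 1.9 and an assumed between-eye correlation of 0.7. The baseline covariate was left out. With both eyes, the mean estimate was 1.72 at u = 20% and 1.52 at u = 40% (simulation standard errors 0.08 and 0.07). In treated eyes only it was 1.93 and 1.88.

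**Step 4. Size against sampling noise.** The 95% half-width is 1.96 × 0.66 = 1.3 mmHg. The loss is 0.10 to 0.38 mmHg for δ = 1.9 and 0.05 to 0.20 mmHg for δ = 1.0, so it lies well inside the interval over the whole assumed range.

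**Step 5. Precision lost by restricting to treated eyes.** Suppose 4.6 is a per-eye SD and the between-eye correlation is 0.7. The variance of a two-eye mean is then 4.6² × (1 + 0.7)/2 = 17.99, and of a single eye 4.6² = 21.16. At u = 20%:

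- Both eyes: standard error √(2 × 17.99/97) = 0.61 mmHg.
- Treated eyes only: information per arm 97 × (0.8/17.99 + 0.2/21.16) = 5.23, so standard error √(2/5.23) = 0.62 mmHg.

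On these assumptions, power for a 1.9 mmHg treated-eye effect is about 80% with all eyes and 87% with treated eyes only.

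**Step 6. Consequence for a later trial.** If it analysed treated eyes but were sized on a diluted estimate, its sample size would be multiplied by 1/(1 - u/2)². At u = 20% this is 1/0.81 = 1.23.

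**The case against.** The strongest objection is that the governing quantity is unknown. No section says how many participants, if any, treat one eye. A reader might infer from the both-eyes rule that untreated eyes are in the analysis and do dilute the effect. The documents support only the conditional statement: entry allows it and the analysis does nothing about it. This objection stands.

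A reader might also take 1.9 mmHg as the effect the trial expects to find. It is the detectable difference, and the plan itself expects a small reduction at most. The absolute loss is then smaller and hard to tell from noise. This stands too.

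It is tempting to say that an eye without drops cannot respond at all. The documents do not establish that. Coaches report to the ophthalmologist, participants take questions to their physician, and visit IOPs reach the health record, so care of either eye could change during the six months. Any effect on the fellow eye would reduce the dilution.

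The all-eyes average is also a legitimate target if the question is the programme's effect on participants' pressure overall. It understates the effect only if the effect in treated eyes is wanted. Keeping it as a sensitivity analysis meets this point.

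The intent-to-treat objection does not stand. Prescription at baseline precedes randomization and everyone eligible takes at least one drop. Each randomized participant therefore keeps at least one eye in the analysis set, and none is removed by arm or outcome.

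**Conclusion.** The point holds in conditional form and is low priority. The plan puts both eyes in the IOP model, entry does not require both to be treated, and nothing elsewhere closes the gap. If a share u of participants treats one eye, the expected arm effect falls by a factor of about (1 - u/2). For assumed u of 10% to 40% that is a loss of 5% to 20% of whatever the treated-eye effect is.

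This rests on no effect in the fellow eye and on an assumed u; at u = 0 the loss is zero. The shrinkage factor does not depend on the SD. The power figures do, and the plan does not say whether 4.6 mmHg is per eye or per person.

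The dilution is toward no effect, so it does not create a false claim of benefit. The primary adherence analysis and the secondary distress analysis are untouched.

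**What to change.** Record at baseline, from the health record, which eye or eyes are prescribed an ocular hypotensive drop. Fit the main IOP mixed model on those eyes, keeping the adjustment for baseline IOP and clinic and the random subject effect. Report the all-eyes model as a sensitivity analysis, and give the observed share of participants treating one eye so that readers can judge the difference.

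The cost is one added data field, a line in the SAP and a small loss of precision (standard error from about 0.61 to 0.62 mmHg in the example above). A reader might assume that the field already exists. The study has access to the health record, and the coaching tool uses each participant's recommended medications, but the documents do not say that the treated eye is captured. If everyone treats both eyes, the two analyses coincide and nothing is lost.

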### **Qualitative Data Analysis**

We will select at least 13 participant interviews (to reach thematic saturation) from each of the following six categories (~78 interviews), and transcribe these verbatim.

Participants who: 1) improved adherence; 2) did not improve adherence; 3) are White; 4) are African American; 5) live under the federal poverty level; and 6) live over the poverty level. We will transcribe all interviews with glaucoma coaches and key health system stakeholders. Two researchers will categorize key ideas and phrases as codes under the five overarching domains of the CFIR framework: intervention characteristics, outer setting, inner setting, characteristics of the individuals involved, and the process of implementation. The domains will be further mapped onto the 24 constructs provided by the CFIR framework. A codebook will be developed, five transcripts will be coded, and inter-coder reliability will be calculated using Nvivo 10.0. If consensus between the two coders cannot be reached, the issue will be adjudicated by a third researcher.

Transcripts will be coded once researchers have achieved >80% agreement on >95% of the codes. [name], an expert in behavioral intervention trials and implementation analyses, will lead this analysis. To assess *effectiveness*, we will analyze transcripts using a mixed-methods approach. We will compare key themes between groups with high and low change in medication adherence and between people by race and income level using a joint display. [name], an expert in disparities in health care experiences, will lead this analysis. To assess barriers and facilitators to future *adoption*, we will analyze SEE Program participants' attitudes with a focus on the CFIR construct "knowledge and beliefs about the intervention" where we assess participant willingness to attend additional office visits for coaching sessions. We will use the CFIR construct "implementation climate" to further explore key health system stakeholder perceptions of barriers and facilitators to both adoption and *maintenance*. Differences in barriers/facilitators across the two study sites will be assessed using joint displays to identify areas for optimization.

### **Sample Size Aim 1: Compare the efficacy of the SEE Program with enhanced standard care in improving glaucoma medication adherence.**

We conducted brief interviews with 25 glaucoma specialists from throughout the US to gauge expert opinion regarding clinically important effect size. Their average recommendation for difference of group proportions of good adherence was 18.5 percentage points (95% CI 15.6-

21.5). Their average recommendation for difference of group mean adherence was 17.7 percentage points (95% CI 14.6-20.8). Additionally, mean medication adherence increased by 20 percentage points in our SEE Program pilot study from 65.7% ( $\pm 10.3$ ) at baseline to 85.7% ( $\pm 11.8$ ) after the program. With 97 participants in each group, a t-test has 80% power to detect a difference of 8 percentage points in mean adherence between the two groups, if the within group standard deviation (SD) is 20 ( $0.40 \times 20 = 8$ ). In our preliminary data the SD was 18, but we anticipate and plan for a possibly more diverse study group (calculated using R 'pwr' package). Our glaucoma specialists were divided on the importance of clinically important effect size, so we plan to be adequately powered for both continuous and binary adherence measures. Their average recommendation for difference of group proportions of good adherence was 18.5 percentage points (95% CI 15.6-21.5). The proposed sample size (n=97 per group) provides 80% power (at two-sided  $\alpha=0.05$ ) for Pearson's Chi Square Test of Independence to find a difference of 20 percentage points for the proportion of patients attaining good ( $\geq 80\%$ ) adherence between the intervention and control groups.

For our secondary outcome, with this sample size, we can detect a 1.1-point difference in mean change in Glaucoma Related Distress (scale 6-18) between trial arms if the SD is 2.8, as it was in our preliminary data. For this sample size in our exploratory outcome, we can detect a 1.9 mmHg difference in mean change in IOP between trial arms if the SD is 4.6 mmHg, as it was in our preliminary data. Although we will make concerted efforts to maximize retention, we will prepare for up to a 20% loss to follow-up as was experienced in our preliminary study and will enroll 115 participants in each arm for a total of 230 participants.

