**Participant Assessments:** After eligibility has been confirmed and informed consent has been obtained, prior to randomization, a research associate will measure participants’ intraocular pressure (IOP), record socio-demographic characteristics, administer a baseline survey including measures of glaucoma-related distress, glaucoma knowledge, perceived competence, motivation, self-efficacy, and autonomy support from their eye care team. IOP measurements will be taken at all in-person study visits. Surveys will be administered by study staff on a tablet with the ability to enlarge the font or have the survey read out loud. Eye drop instillation will be video-recorded. Additionally, we will use commercially available inertial measurement unit sensors (Xsens-dot, Movella, Netherlands) to assess the kinematics of all eye drop instillations. The sensor will be attached to the bottom of the artificial tear by a custom made silicone sleeve and will not interfere with the dispensing of the artificial tears. Snellen visual acuity will be recorded on all participants. Humphrey visual field testing (SITA Fast, 24-2) will be performed on participants who have not had a reliable visual field (SITA, 24-2) within the last year. Participants will be randomized to the SEE Program (experimental) or enhanced standard care by the physician with additional written education materials (control). Medication adherence will be monitored electronically for all participants from baseline through the end of the 6-month program period. A baseline measure of medication adherence will be obtained by an objective method (medication possession ratios assessed from pharmacy refill data for six months prior to study participation) and subjective method (survey). After six-months, a research associate will video-record eye drop instillation, administer a survey with the same behavioral and psychosocial measures and a quantitative program evaluation, and then a masked research associate will measure IOP and conduct a 15-30 minute semi-structured interview with participants in the SEE Program arm to assess their experience with the program. Additionally, we will call participants that do or did not return for the exit visit to ask if they will complete the exit surveys over the phone. All data will be entered into the REDCap

---

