## OUTCOMES

**Primary Outcome:** Six-Month Medication Schedule Adherence. Medication adherence will be measured objectively using electronic monitors with a bottle-in-bottle technique where all glaucoma medications are placed inside electronic pill bottles. When the bottle cap is removed, the time and date stamp is sent to our database. An adherent event is defined as using an eye drop medication within a specified time window of a dose on the previous day. For example, for an eye drop medication dosed once per day, an adherent event is defined as taking the medication within  $24 \pm 4$  hours of the previous day's dose. We include this time window because the biological efficacy of eye drop medications decline when not taken on time. We will compare the current day's doses to the previous day's corresponding doses, ensuring that opening a bottle multiple times prior to a clinic visit does not inflate the adherence metric. Adherence will be calculated as the proportion of doses taken on time divided by total doses prescribed over the six-month study period. For participants on more than one medication,

adherence will be first measured at the medication level and then aggregated to the person level by dividing the total number of doses of all medication(s) taken on time by the total number of doses prescribed. Our primary outcome is the mean adherence in the control and intervention groups. We will also assess the proportion of patients who are  $\geq 80\%$  adherent.

**Secondary Outcome:** Glaucoma-related Distress. Glaucoma-related distress, or the emotional distress participants experience related to having glaucoma, will be measured using the Diabetes Distress Scale adapted for glaucoma (Cronbach's  $\alpha = 0.93$ ). The Diabetes Distress Scale consists of 17 items with four subscales that measure emotional burden (5 items), physician-related distress (4 items), regimen-related distress (5 items), and diabetes-related interpersonal distress (3 items). In our pilot validation study of three items from the regimen-related distress and emotional burden subscales in a glaucoma population, we found a significant association of increased glaucoma-related distress with poor electronically monitored glaucoma medication adherence (adjusted  $\beta = -2.47$ , standard error (SE) = 0.61,  $p=0.0001$ ).

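### Enrolling 115 per arm and losing 20% leaves 92 per arm, not the 97 on which the power statements rest; the effect is small and the fix is wording

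*Combined protocol and SAP*

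**What the plan says.** All the numbers are in the combined protocol and SAP, mainly under Sample Size Aim 1.

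- Primary outcome: "With 97 participants in each group, a t-test has 80% power to detect a difference of 8 percentage points in mean adherence", for a within-group SD of 20. The preliminary SD was 18.
- Binary adherence measure: "The proposed sample size (n=97 per group) provides 80% power" for a 20-point difference in the proportion with good adherence, at two-sided 0.05. No control rate is given.
- Secondary outcome, at the same sample size: "we can detect a 1.1-point difference in mean change in Glaucoma Related Distress (scale 6-18) between trial arms if the SD is 2.8".
- Exploratory outcome, at the same sample size: "we can detect a 1.9 mmHg difference in mean change in IOP between trial arms if the SD is 4.6 mmHg".
- Enrolment: the study will "prepare for up to a 20% loss to follow-up as was experienced in our preliminary study and will enroll 115 participants in each arm", 230 in total.

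Sample Size Aim 2 uses 97 per arm again. The document does not show how 115 was obtained from 97.

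**The concern.** An allowance for loss should leave the number on which power was calculated once the stated loss has occurred. Here it does not: at the loss the plan says it prepares for, and saw in its preliminary study, fewer than 97 per arm remain. A reader would take a 20% loss as fully covered when the cover ends at 15.7%. The same 97 supports the primary, binary, distress, IOP and Aim 2 statements, so each has to be checked at the smaller number. At stake is whether the stated power figures are accurate; the design itself is not in question.

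**Working it through.** **Inputs** (Sample Size Aim 1): 97 per arm for power; 115 per arm enrolled; loss up to 20%; 8 points at SD 20 (preliminary SD 18); 20 points for the binary measure; distress 1.1 at SD 2.8; IOP 1.9 mmHg at SD 4.6; specialists' mean difference 17.7 points.

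**Assumptions.** Two-sided 0.05 is stated only for the binary test and is taken to apply throughout. The detectable differences for distress and IOP are taken to be at 80% power. Lost participants give no outcome data.

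**1. The plan's own figure.** Two-sample t-test, standardized difference 8/20 = 0.40, noncentral t distribution with noncentrality 0.40 × √(n/2).
- n = 97: noncentrality 2.79, power 79.2%. This agrees with the stated 80% after rounding; a full 80% needs slightly over 99 per arm.
- Binary measure, pooled-variance normal test, 40% vs 60% (assumed; the least favourable 20-point pair): 80.0% at 97, as stated.

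**2. The allowance for loss.**
- Remaining after 20% loss: 115 × 0.80 = 92 per arm (23 lost), 184 in total.
- Largest loss that keeps 97: (115 − 97)/115 = 18/115 = 15.7%.
- Enrolment that keeps 97 after 20% loss: 97/0.80 = 121.25, so 122 per arm.
- Multiplying instead of dividing gives 97 × 1.20 = 116.4, close to 115. That may be how 115 arose, but this is a guess.

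**3. Consequences at 92 per arm.**

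| Quantity | 97 per arm | 92 per arm |
|---|---|---|
| Power, 8 points, SD 20 | 79.2% | 77.0% |
| Difference with 80% power, SD 20 | 8.09 | 8.31 |
| Power, 8 points, SD 18 | 86.9% | 85.0% |
| Power, 17.7 points, SD 20 | >99.9% | >99.9% |
| Binary, 40% vs 60% | 80.0% | 77.9% |
| Binary, control 30% or 50% | 81.7% | 79.6% |
| Binary, control 20% or 60% | 86.6% | 84.7% |
| Distress: difference with 80% power | 1.13 | 1.16 |
| Distress: power for 1.1 | 77.7% | 75.5% |
| IOP: difference with 80% power (mmHg) | 1.86 | 1.91 |
| IOP: power for 1.9 mmHg | 81.7% | 79.6% |

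The control rates are assumptions.

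**4. Splitting the gap for the primary outcome.** The gap to 80% at 92 per arm is 80.0 − 77.0 = 3.0 points. Of this, 80.0 − 79.2 = 0.8 is the plan's rounding at 97, and 79.2 − 77.0 = 2.2 comes from the loss.

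**5. Aim 2, for orientation.** Take the R² increase of 0.04 for the moderator with no other explained variance (a conservative assumption), so f² = 0.04/0.96, with 1 and N − 4 degrees of freedom. Power is 80.8% at N = 194 and 78.6% at N = 184. The mediation calculation was not rerun.

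**The case against.** The arithmetic is not in dispute; the case on the other side is about how much it matters.

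- **20% is an upper bound, and SD 20 is cautious.** True. The shortfall starts only above 15.7% loss, and at 92 per arm power for 8 points reaches 80% once the SD is about 19.3 or less. But a plan that prepares for 20% should deliver its stated figures at 20%.
- **Lost participants may still contribute.** Under Outcomes, "Adherence will be calculated as the proportion of doses taken on time divided by total doses prescribed over the six-month study period". The Statistical Analysis Plan says "We will perform intent-to-treat analysis of all randomized participants to evaluate our primary, secondary and exploratory outcomes". Under Participant Assessments, "we will call participants that do or did not return for the exit visit to ask if they will complete the exit surveys" by phone. If all 115 per arm contributed, power for 8 points at SD 20 would be 85.6%. This stands as a possibility. However, no explicit rule says how incomplete monitoring is handled, and enlarging 97 to 115 makes sense only if lost participants give no data.
- **Some figures barely move.** This stands. The IOP figure still holds as printed, and the binary measure falls clearly short only near 40% vs 60%.
- **The planned distress analysis is more precise than the one powered.** The power statement concerns mean change, whereas the analysis regresses the exit score on treatment adjusted for baseline. Suppose 2.8 is the SD of change and the variance is equal at both visits. Adjustment then multiplies the change-score variance by (1 + r)/2, where r is the baseline-exit correlation. Power for 1.1 at 92 per arm would be 86% at r = 0.5, 82% at 0.7 and 78% at 0.9. The document gives no r, so this cannot be settled. A restated distress figure should therefore be labelled as referring to mean change, the basis the section itself uses.

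**Conclusion.** The point holds. With 115 enrolled per arm and 20% lost, 92 remain, and nothing elsewhere in the document reconciles this with 97. The cost is about 2 points of power on most measures: 77.0% instead of 79.2% for 8 points at SD 20, or a detectable difference of 8.3 instead of 8.1 points. It rests on a loss at the plan's upper bound and on lost participants giving no outcome data. The primary comparison keeps 85.0% power at the preliminary SD and is amply powered for the difference the specialists recommended. The figures should be corrected, but the correction is minor.

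**What to change.** Keep 230 and correct Sample Size Aim 1 in one of two ways.

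**(a) Change the loss statement.** Suggested text: *Enrolling 115 per arm retains at least 97 per arm if no more than 18 per arm (15.7%) are lost to follow-up, which is less than the 20% seen in our preliminary study.* The 97-based figures and Sample Size Aim 2 then stay as they are. This suits a team that expects better retention than in its preliminary study, and it should say why.

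**(b) Keep the 20% and restate the figures.** Suggested text: *At 20% loss, 92 per arm remain if lost participants give no outcome data. At two-sided 0.05 this gives about 77% power for 8 points in mean adherence (SD 20), or 80% power for 8.3 points, and about 78% power for 40% vs 60% with good adherence (assumed rates). With 80% power, differences in mean change of about 1.2 points in distress (SD 2.8) and 1.9 mmHg in IOP (SD 4.6) are detectable.* The Aim 2 calculations should then be rerun at 92 per arm and their results printed.

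Replacing 97 by 92 beside the 80% claims without recalculating would only create a new error.

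Cost: (a) is wording only. (b) is wording, a rerun for Aim 2, and a stated power of about 77% rather than 80% for 8 points. Neither needs extra patients or changes the design or analysis.
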